## 4 STUDY DESIGN

### 4.1 Overall Design

This is a Phase 1, open-label, multisite, dose escalation study of nemtabrutinib in Japanese participants with Mature B-cell neoplasms who have failed or are intolerant to previous treatment. This study will evaluate the safety, tolerability, PK and preliminary efficacy of nemtabrutinib.

The study design is shown in [Figure 1](#). This study will enroll patients according to a modified toxicity probability interval (mTPI) design and perform dose escalation of nemtabrutinib at each predetermined dose levels (45 mg QD or 65 mg QD). To evaluate the DLT, participants will be enrolled to one dose level at the same time. Study medication will be administered at the following dose levels;

- Dose level 1 (DL1): 45 mg QD
- Dose level 2 (DL2): 65 mg QD

Details of DLT assessment schedules and rules are described in Section 4.3.2. The definition of DLTs is provided in Section 4.3.1. In principle, during DLT assessment period, participants will be hospitalized.

AEs will be evaluated by the investigator, according to criteria outlined in the NCI-CTCAE, version 5.0, to establish the safety and tolerability of nemtabrutinib monotherapy per the primary objective of this study.

Secondary objectives of this study are to evaluate PK following administration of nemtabrutinib and to evaluate ORR and DOR assessed by the investigator using assessment criteria of each disease as a preliminary efficacy evaluation. PFS and OS assessed by the investigator using assessment criteria of each disease are evaluated as tertiary/exploratory objectives.

Treatment response assessments may include computed tomography (CT)/magnetic resonance imaging (MRI) and/or positron emission tomography (PET) imaging, and laboratory assessments. Treatment response assessments will be performed during screening, every 12 weeks ( $\pm 7$  days), and every 24 weeks ( $\pm 7$  days) after 4 years and should follow calendar days from C1D1.

Patients will continue taking nemtabrutinib 45 mg or 65 mg QD until unacceptable toxicity, disease progression, or another discontinuation criterion described in Section 7.1 is met.

In or after cycle 4, participants receiving 45 mg of nemtabrutinib may be escalated to the 65 mg if the tolerability is confirmed at the 65 mg of nemtabrutinib and at the discretion of the investigator after discussion with the participant, upon the consultation with the sponsor.

Participants who discontinue treatment for reasons other than confirmed progressive disease will have posttreatment follow-up for disease status (including imaging) until progressive

disease, initiating a new anticancer therapy, withdrawing consent for study participation, pregnancy, or becoming lost to follow-up.

Participants who experience the confirmed disease progression or start a new anticancer therapy will move into the Survival Follow-up Phase and should be contacted by telephone approximately every 12 weeks (84±14 days) to assess for survival status until death, withdrawal of consent, or the end of the study, whichever occurs first.

After approval of Protocol amendment 04, participants in the Survival Follow-up phase will be discontinued from the study and no further visits will be required.

No interim analysis is planned for this study.

Specific procedures to be performed during the study, including prescribed times and associated visit windows, are outlined in Section 1.3 of the SoA. Details of each procedure are provided in Section 8.

## **4.2 Scientific Rationale for Study Design**

This is a Phase 1, open-label, multisite, dose escalation study designed to evaluate the safety and tolerability of nemtabrutinib, a non-covalent irreversible inhibitor of BTK, in Japanese participants with Mature B-cell neoplasms who have failed or are intolerant to previous treatment (either at least 2 prior regimens given in combination or sequentially or 1 prior BTK-containing regimen when a BTK inhibitor is approved as first line therapy). BTK inhibitors are approved for the treatment of CLL/SLL; however, resistance is known to develop to these irreversible inhibitors, with one of prevalent mechanism being the acquisition of BTK-C481 mutations. There is a need for more effective therapies for patients who have failed 1 or more prior therapies. Nemtabrutinib can inhibit wild-type BTK as well as the BTK-C481 mutant form of the enzyme. In the CLL/SLL indication resistance mutations occur in approximately 40 to 80% of patients following treatment with covalent, irreversible inhibitors (e.g., ibrutinib) [Gango, A., et al 2020] [Quinquenel, A., et al 2019] [Woyach, J. A., et al 2017] [Kanagal-Shamanna, R., et al 2019]. Data from the first-in-human Phase 1 study of nemtabrutinib has shown response in a variety of hematological malignancies, including CLL/SLL.

### **4.2.1 Rationale for Endpoints**

#### **4.2.1.1 Efficacy Endpoints**

Endpoint definitions are provided in Section 9.4.1.

#### **Objective Response**

OR is the secondary efficacy endpoint.

Treatment effect measured by OR can represent direct clinical benefit based on the specific disease, context of use, magnitude of the effect, number of CRs, durability of response, disease setting, location of the tumors, available therapy, and risk-benefit relationship.

Treatment effect measured by OR can be a surrogate endpoint to support accelerated approval according to FDA guidance (Clinical Trial Endpoints for the Approval of Cancer Drugs and Biologics Guidance for Industry, Dec 2018). Nodular partial remission (nPR) has all the features of a CR but has lymphoid nodules in the marrow, which should be further evaluated. If immunohistochemistry conclusively shows the nodules are CLL cells, a response of “nPR” should be assigned. If analysis shows them to be composed of other histological types, it should be considered CR [Hallek, M., et al 2018].

Each hematological malignancy has specific response criteria that will be applied in the assessment of OR as summarized in Section 3.

### **Duration of Response**

DOR is a secondary efficacy endpoint.

Improved DOR can result in a meaningful delay in disease progression as opposed to a temporary response without lasting benefit.

### **Exploratory Efficacy Endpoints**

OS represents a precise and reliable measure of time to event endpoint. PFS is a surrogate endpoint that reflects tumor growth and includes deaths and therefore correlates to OS. Undetectable MRD is a surrogate endpoint for CLL and current literature suggests that there is an association between MRD negativity and OS in patients with CLL treated with chemoimmunotherapy. The therapeutic paradigm with small molecule inhibitors of the B-cell receptor signaling pathway and other novel products continue to rapidly evolve in this area [Food and Drug Administration 2020]. PRL represents a reduction in lymph nodes, splenomegaly and other markers of response with no sign of progression other than lymphocytosis, and has been used in other BTKi studies. Partial response with lymphocytosis is defined as a >50% reduction in lymphadenopathy and splenomegaly, with persistent lymphocytosis; often the blood lymphocyte counts are equal to or greater than those observed prior to therapy [Kipps, T. J., et al 2017]. Minor response (MR) is defined as 25 to 49% reduction in serum IgM levels [Dimopoulos, M. A., et al 2014].

#### **4.2.1.2 Safety Endpoints**

The primary objective of this study is to evaluate the safety and tolerability of nemtabrutinib in patients with Mature B-cell neoplasms who have failed or are intolerant to previous treatment in Japanese patients. The primary safety analysis will be based on participants who experience toxicities as defined by NCI-CTCAE version 5.0 criteria. Safety will be assessed by evaluating the toxicities and grades of toxicities experienced by participants who have received nemtabrutinib.

For AEs, attribution to drug, time-of-onset, duration of the event, its resolution, and any concomitant medications administered will be recorded. Adverse events that will be analyzed include, but are not limited to, all AEs, SAEs, fatal AEs, and laboratory changes.

#### **4.2.1.3 Pharmacokinetic Endpoints**

The secondary objective of this study is to assess PK profile with single administration of nemtabrutinib. PK variables determined will include AUC, Cmax, Cmin, Tmax, and when possible t1/2. Blood samples for PK analysis will be drawn during the first three cycles of nemtabrutinib administration for each dose level. Additional unscheduled blood sample(s) for PK may be collected on any study day(s) upon agreement between the investigator and Sponsor.

#### **4.2.1.4 Pharmacodynamic Endpoints**

The BTK signaling biomarkers and/or other BCR signaling pathway related cytokines will be evaluated.

#### **4.2.1.5 Planned Exploratory Biomarker Research**

The mechanism of action of many antitumor agents is not completely understood and much remains to be learned regarding how best to leverage new drugs in treating patients. Thus, to aid future patients, it is important to investigate the determinants of response or resistance to cancer treatments. These efforts may identify novel predictive/pharmacodynamic biomarkers and generate information that may better guide single-agent and combination therapy with antineoplastic drugs. To identify novel biomarkers, biospecimens (eg, blood components, tumor material, etc.) will be collected to support analyses of cellular components (eg, protein, DNA, RNA, metabolites) and other circulating molecules. Investigations may include, but are not limited to the following:

*Germline genetic analyses (eg, SNP analyses, whole exome sequencing, whole genome sequencing)*

This research may evaluate whether genetic variation within a clinical study population correlates with response to the treatment(s) under evaluation. If genetic variation is found to predict efficacy, the data might inform optimal use of therapies in the patient population. Furthermore, it is important to evaluate germline DNA variation across the genome to interpret tumor-specific DNA mutations.

### **4.3 Justification for Dose**

The starting dose is 45 mg, which is the highest dose in which no DLTs were observed in MK-1026-001 (BELLWAVE-001) study, to evaluate the safety and tolerability of nemtabrutinib for Japanese participants as this study is a first clinical trial for nemtabrutinib in Japan. The dose level will be escalated to 65 mg QD based on the dose escalation design if the dose level of 45 mg QD is tolerable. Further information on dose modifications is provided in Section 6.6.1.

Part 1 of MK-1026-003 (BELLWAVE-003) study consisted of dose escalation and dose confirmation to establish the RP2D of nemtabrutinib. Dose escalation was based on a modified toxicity probability interval design. Dose escalation and de-escalation decisions were based on the number of participants enrolled and number of DLTs observed. PK, PD,

efficacy and safety data for 23 participants with CLL/SLL (dosed with 80 mg) in the BELLWAVE-003 study (24-MAY-2022 data cutoff), and 138 CLL/SLL and NHL participants enrolled in the BELLWAVE-001 study (doses ranging from 5 to 75 mg), including 112 participants enrolled in the 65 mg arm (08-APR-2022 data cutoff), were used to determine the RP2D.

An evaluation of efficacy showed a clear dose-dependent increase in the ORR with doses up to 75 mg QD in the BELLWAVE-001 and a similar benefit at a dose of 80 mg QD in the BELLWAVE-003 study. A total of 112 participants received at least 1 dose of 65 mg nemtabrutinib in the BELLWAVE-001 study. A total of 57 participants treated with 65 mg nemtabrutinib had CLL/SLL. The median follow-up for the 57 CLL/SLL treated with 65 mg nemtabrutinib was 8.1 months (range 0.1 to 38.8 months). The efficacy results showed ORR of 56.1% (95% CI: 42.4, 69.3). The ORR excluding PRL was 29.8%. Of the CLL/SLL participants, 2 (3.5%) achieved a complete remission, 15 (26.3%) achieved a PR and 16 (28.1%) achieved SD.

A total of 6 participants treated at 65 mg QD reported 8 DLTs, 7 were considered related to nemtabrutinib and 1 not related per investigator. Of these 6 participants, 1 participant experienced neutropenia (Grade 4), 1 participant experienced neutropenia twice (Grade 2 and Grade 3), 1 participant experienced thrombocytopenia (Grade 4), 1 participant experienced erythematous rash (Grade 3), 1 participant experienced pruritus (Grade 3) and maculopapular rash (Grade 3), and 1 participant experienced supraventricular tachycardia (Grade 3).

The most common ( $\geq 10\%$ ) treatment-related AEs observed across all doses included dysgeusia (18.4%), neutrophil count decreased (17.6%), nausea and fatigue (both at 12.5% each), and platelet count decreased (10.3%). SAEs were reported in 47.1% participants, of which, 8.1% were assessed by the investigator as treatment related. SAEs that were assessed by the investigator as related to nemtabrutinib included 2 cases of rash maculo-papular and singular events of febrile neutropenia, bradycardia, supraventricular tachycardia, diarrhea, cellulitis, blood creatinine increased, lipase increased, neutrophil count decreased, drug reaction with eosinophilia and systemic symptoms and rash erythematous. A total of 28 (20.6%) participants discontinued study treatment due to an AE; 16 (11.8%) were considered to be related to study treatment. There were 7 reported deaths; none were assessed as related to nemtabrutinib or met the definition of DLT. Of the 7 deaths, 3 were due to acute respiratory failure and 1 each from respiratory failure, dyspnea, fall and sepsis. Overall, no new safety issues were identified; observed events were consistent with the class and as expected in the underlying population.

Important potential AEs based on drug class (eg, hemorrhages, hypertension, atrial fibrillation, infection, cytopenias, and hypersensitivity) have been observed across the BELLWAVE-001 and BELLWAVE-003 studies and are generally seen at lower incidences compared to the frequencies, severity, and seriousness observed with ibrutinib. These observed events did not have significant impact on discontinuations and interruptions.

CCL3, a BCR-dependent chemokine shown to be downregulated upon inhibition of BTK, was used as a PD marker in both BELLWAVE-001 and BELLWAVE-003 studies. Analysis of the PD data showed a dose-dependent decrease in serum CCL3 concentrations with

increasing nemtabrutinib dose. PK data showed an increase in exposure across the nemtabrutinib dose range from 5 mg to 80 mg QD. The clearance following single and multiple dosing was generally similar across the dose range and also across days (Day 1 and Day 22) suggesting that nemtabrutinib exhibits linear PK. Also, considering the preclinical data obtained to date [Section 2.2.2.2] that CCI [REDACTED] here is unlikely to occur potential differences of PK in Japanese CCI [REDACTED] derived from ethnicity/race.

Based on the totality of data reviewed (including safety, efficacy, PK, PD, and nonclinical toxicology), the benefit/risk profile favors 65 mg QD. Therefore, the RP2D for nemtabrutinib is 65 mg QD.

#### 4.3.1 Dose-limiting Toxicity Definition

All toxicities will be graded using NCI-CTCAE version 5.0 based on the investigator assessment. Hematologic toxicities in participants with CLL will be assessed according to the iwCLL criteria as described in Appendix 11.

The DLT window of observation will be during Cycle 1 (4 weeks).

The occurrence of any of the following toxicities during Cycle 1 will be considered a DLT, if assessed by the investigator to be possibly, probably, or definitely related to study intervention administration.

- Grade  $\geq 3$  nonhematologic toxicity with exception of Grade 3 nausea, vomiting, diarrhea, rash, fatigue, and uncontrolled hypertension which will not be considered a DLT unless lasting more than 72 hours despite optimal supportive care (not laboratory)
- Grade 4 hematologic toxicity lasting  $>7$  days, OR
  - Grade 4 platelet count decreased of any duration
  - Grade 3 platelet count decreased if associated with bleeding

Note: For participants with BM involvement, numerical value of decreased platelet count for Grade 3 or Grade 4 will not be considered DLT unless the participant developed new or worsening clinical symptoms based on investigator assessment as compared with baseline and associated with low platelet counts. Grade 3 lymphocytosis, considered to be an expected outcome of BTK inhibition, is not considered a DLT.

- Grade 3 or higher febrile neutropenia of any duration

- Any Grade 3 or Grade 4 nonhematologic laboratory abnormality, if:
  - Values result in DILI (see Section 8.4.7 for laboratory criteria), or
  - Medical intervention is required, or
  - The abnormality leads to hospitalization, or
  - The abnormality persists for >1 week

Exceptions: Clinically nonsignificant, treatable, or reversible laboratory abnormalities including liver function tests, uric acid, etc. (see Section 8.4.1).

- Missing >25% of nemtabrutinib doses as a result of drug-related AE(s) during the first 1 cycle (4 weeks)
- Grade 5 toxicity

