Out of 24 DLT-evaluable participants, 5 participants reported DLTs including cardiac failure (Grade 3 in 1 participant), hepatic function abnormal (Grade 3 in 1 participant), drug eruption (Grade 3 in 2 participants), and hematoma (Grade 3 in 1 participant) and intracranial hemorrhage (Grade 5 in 1 participant). All DLTs occurred within the 8-week DLT observation period, except 1 occurrence of Grade 3 hematoma (occurring on Study Day 59) and Grade 5 intracranial hemorrhage (occurring on Study Day 61). Both cases of drug eruptions and the first occurrence of hematoma resolved after 6 days to 2 weeks. The other DLTs (second occurrence of hematoma, hepatic function abnormal, and cardiac failure) had not resolved at the time of the data extraction. Although the current DLT rate is 20.8% (5 out of 24 participants), this is below the target DLT rate of 30%, new DLTs occurred at the 80 mg dose level that were not observed at the 65 mg dose level, except for drug eruption. Additionally, 1 participant experienced Grade 3 urinary tract infection that was deemed a DLT; however, due to data entry error, this DLT was not included in this data extraction. This event occurred on study day 23 and resolved after 1 week. The corrected DLT rate including this additional DLT participant was 25% (6 out of 24 DLT-evaluable participants).

The most common AEs (>10%) were constipation (26.3%); peripheral edema (21.1%); dysgeusia (18.4%); anemia and fatigue (15.8% each); pyrexia (13.2%); and ALT increased, AST increased, COVID-19, cough, and upper respiratory tract infection (10.5% each). Of the 38 participants, 24 (63.2%) had at least 1 Grade 3 to 5 TEAE, of which 15 (39.5%) were assessed by the investigator as related. Grade 3 to 5 TEAEs occurring in 5% participants included anemia (13.2%); COVID-19, sepsis, and thrombocytopenia (7.9% each); and drug eruption, febrile neutropenia, GGT increased, hematoma, hepatic function abnormal,

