#### 4.3.2 Dose Finding Using a Modified Toxicity probability Interval Design

Further dose finding will follow the mTPI design [Ji, Y., et al 2007] with a target DLT rate of 30%. Dose escalation and de-escalation decisions are based on the mTPI design and depend on the number of participants enrolled and number of DLTs observed at the current dose level.

A minimum of 3 participants are required at each dose. However, depending on the actual DLT rate, 3 to 6 participants may be enrolled. In Table 2, the columns indicate the numbers of participants treated at the current dose level, and the rows indicate the numbers of participants experiencing DLT. The entries of the table are the dose finding decisions: E, S, D, and DU represent escalating the dose, staying at the same dose, de-escalating the dose, and excluding the dose from the study due to unacceptable toxicity, respectively. Notably, given a flat non-informative prior Beta(1,1), the DU decision occurs when the posterior probability that the toxicity rate at the current dose level is larger than the target toxicity rate of 30% is greater than 95%.

When adding participants to a dose level in response to a “stay” decision, the number of additional participants to be enrolled is capped to minimize the exposure to a dose that may be unacceptably toxic (denoted as DU in Table 2). Second, to determine how many more participants can be enrolled at the dose level, one can count steps in diagonal direction (down and to the right) from the current cell to the first cell marked DU. For example, if 1 of 3 participants have experienced a DLT at a given dose level, no more than an additional 3 participants should be enrolled at this dose level until additional DLT data are available. This is because this dose level would be considered unacceptably toxic if all 3 of the additional participants experience a DLT (ie, 4/6 participants with DLT in Table 2).

A D or DU decision at the lowest dose level will stop the enrollment and sponsor will discuss the continuation of the study. An E decision at the highest dose level will result in staying at that level.

If 1 out of initial 3 participants develop a DLT, it will be S, therefore 3 participants will be added. If 2 out of 3 participants develop a DLT, it will be D, where the dose should be reduced. If 2 out of 6 participants develop a DLT, sponsor and principal investigator will discuss path forward of further Japanese enrollment.

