### **6.1.1 Treatment**

Nemtabrutinib is administered as a daily 45 mg or 65 mg dose, taken orally, until disease progression, unacceptable toxicity, or another discontinuation criterion is met.

Each cycle consists of 4 weeks (28 calendar days). If a dose interruption or delay occurs or persists on Day 1 of planned next cycle the current cycle will be longer than 28 calendar days. If a dose interruption or delay occurs in the middle of the cycle and treatment can be resumed on Day 1 of planned next cycle, the current cycle will remain 28 days.

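### The laboratory exception in Section 4.3.1 conflicts with the DILI and medical-intervention triggers above it, so a related Grade 3/4 event that reverses may or may not count as a DLT

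*Combined protocol and SAP*

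**What the plan says.** Section 4.3.1 lists the toxicities that count as DLTs in Cycle 1 when the investigator considers them possibly, probably or definitely related. For Grade 3 or 4 nonhematologic laboratory abnormalities it gives four alternative triggers. Two matter here: "Values result in DILI (see Section 8.4.7 for laboratory criteria), or" and "Medical intervention is required, or". The others are hospitalization and persistence beyond one week. Directly below comes the exception: "Exceptions: Clinically nonsignificant, treatable, or reversible laboratory abnormalities including liver function tests, uric acid, etc", with a reference to Section 8.4.1.

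A separate bullet makes missed dosing a DLT: "Missing >25% of nemtabrutinib doses as a result of drug-related AE(s) during the first 1 cycle (4 weeks". Section 8.4.7 gives the DILI thresholds: AST or ALT at least 3 times ULN, total bilirubin at least 2 times ULN and alkaline phosphatase below 2 times ULN. Such events must be reported within 24 hours as both an ECI and an SAE.

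The DLT count drives Table 2. Section 4.3.2 spells out one case: "If 1 out of initial 3 participants develop a DLT, it will be S, therefore 3 participants will be added".

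**The concern.** The exception and the triggers cover the same ground. An abnormality that is treatable is likely to be one for which treatment was needed, which is a trigger. An abnormality that is reversible and shows in liver tests may be one that met the DILI criteria, which is another trigger. The word *or* makes the three qualifiers alternatives, so clinical nonsignificance does not restrict the other two. Other carve-outs in Section 4.3.1 carry limits: certain Grade 3 events count again if they last more than 72 hours despite supportive care, and low platelets with marrow involvement count if new or worsening symptoms appear. The laboratory exception has no such limit.

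DLT is the first primary endpoint and the only toxicity count that Table 2 uses. The study is multisite and Section 1.1 lists no adjudication committee, so two sites could classify the same event differently and both be following the text.

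**Working it through.** **1. Does another section settle precedence?** Section 8.4.1 and its Table 10 give collection periods and reporting time frames. Table 10 has a row for potential DILI events, but it concerns reporting as ECI and SAE. Section 8.4.7 gives thresholds and reporting duties. The first bullet of 4.3.1, on Grade 3 or higher nonhematologic toxicity, sets laboratory events aside. None of these says whether the exception or a trigger wins.

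**2. Which events are exposed?**

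- *Grade.* The laboratory bullet covers Grade 3 and 4 only. An event below Grade 3 is not a DLT under it on either reading.
- *Missed doses.* Cycle 1 has 28 daily doses and 25% of 28 is 7. More than 25% therefore means 8 or more missed doses, which is a DLT on either reading.
- *Grade 4 found early.* Table 6 requires permanent discontinuation for related Grade 4 nonhematologic, non-skin toxicity other than nausea, vomiting or diarrhea. From the Day 8 draw, 28 − 7 = 21 doses are lost; from Day 15, 28 − 14 = 14. Both exceed 7, so both are DLTs by the missed-dose bullet.
- *What remains.* Related Grade 3 events that reverse with 7 or fewer missed doses are left, plus some events found late. A hold starting at the Day 22 draw loses at most 28 − 21 = 7 doses if Cycle 1 is 4 weeks. Under Section 6.1.1, however, when a hold persists "on Day 1 of planned next cycle the current cycle will be longer than 28 calendar days", so an eighth missed dose might count. The late case depends on that reading.

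**3. An example that does not depend on cycle length.** A related Grade 3 event meeting the 8.4.7 criteria is found at the scheduled Day 8 chemistry. Table 6 requires a hold until Grade 1 or baseline. Dosing restarts on Day 15.

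- Missed doses: Days 8 to 14, so 7/28 = 25.0%, which is not more than 25%.
- Duration: not more than one week, so the persistence trigger is not met.
- Doses received: 21/28 = 75.0%, which is not below the 75% replacement threshold in Section 5.5, so the participant stays evaluable.

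If the triggers prevail, this is a DLT. If the exception prevails, it is an evaluable participant without a DLT.

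**4. What one such event does at 45 mg.** Inputs from Table 2: target 0.30, prior Beta(1,1), ε1 = 0.03, ε2 = 0.01, hence intervals (0, 0.27), (0.27, 0.31) and (0.31, 1). The decision is the interval with the largest posterior probability per unit length, with DU if P(p > 0.30) exceeds 0.95. This rule reproduces all 22 entries of Table 2, and the Beta quantiles reproduce all 11 intervals of Table 12.

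- *0/3, posterior Beta(1,4).* P(p > q) = (1 − q)^4, which is 0.2840 at 0.27 and 0.2267 at 0.31. E: (1 − 0.2840)/0.27 = 2.65. S: (0.2840 − 0.2267)/0.04 = 1.43. D: 0.2267/0.69 = 0.33. Decision E. P(p > 0.30) = 0.7^4 = 0.240.
- *1/3, posterior Beta(2,3).* P(p > q) = (1 − q)^4 + 4q(1 − q)^3, which is 0.7041 at 0.27 and 0.6340 at 0.31. E: (1 − 0.7041)/0.27 = 1.10. S: (0.7041 − 0.6340)/0.04 = 1.75. D: 0.6340/0.69 = 0.92. Decision S. P(p > 0.30) = 0.2401 + 4 × 0.3 × 0.343 = 0.652.

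| Reading | Count | Table 2 | DLT rate (90% credible interval) |
|---|---|---|---|
| Exception prevails | 0/3 | E: open 65 mg | 0.000 (0.013, 0.527) |
| Triggers prevail | 1/3 | S: add 3 at 45 mg | 0.333 (0.098, 0.751) |

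**The case against.** The strongest reply is that the text can be made to work. A line headed as exceptions ordinarily overrides the rule it follows, and the triggers would still catch abnormalities that neither respond to treatment nor reverse. Alternatively, the exception names liver function tests and not DILI, which is defined separately. On that view DILI-criteria events stay DLTs, and only isolated liver-test or uric acid changes are excepted.

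This stands in part. A reader might infer that no ordering leaves both clauses with any effect, and the documents do not support that. But the two workable readings give opposite answers for a DILI-criteria event that reverses, and the protocol does not choose between them. The first also drops from the primary endpoint an event reportable within 24 hours as serious, without saying that this is intended.

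The consequences are also cushioned. The sponsor hears of a DILI-criteria event within 24 hours, Section 5.5 has it assess all safety information, and Section 4.3.2 allows escalation to be adjusted on emerging safety data. These can temper a dose decision. They do not say which count enters Table 2 or the DLT listing under Section 9.6.1.

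**Conclusion.** The conflict is real, narrow and cheap to remove. It reaches a related Grade 3/4 laboratory event that meets the DILI criteria or needs treatment and then reverses with 7 or fewer missed doses. Among the first 3 participants at 45 mg, one such event decides between escalating and adding 3 participants, and between a reported rate of 0.000 and 0.333. Neither Table 2 nor Table 12 contains an error; only the count fed into them is in doubt.

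Two stronger inferences should be resisted. A reader might conclude that any DILI-criteria event can disappear from the count. The Grade 3/4 limit, the missed-dose bullet and Table 6 prevent that for many of them. A reader might also look for a frequency in BELLWAVE-003, where 1 of 24 DLT-evaluable participants had a Grade 3 hepatic function event. That was at 80 mg with an 8-week window, and it was counted as a DLT. It is not said to have met the DILI criteria, and the summary states: "The other DLTs (second occurrence of hematoma, hepatic function abnormal, and cardiac failure) had not resolved at the time of the data extraction". An unresolved event says nothing about reversible ones. The frequency is unknown and probably low, and no rate should be attached to it.

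The size given assumes that the site considers the event related and that the exception is applied as literally worded.

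**What to change.** In Section 4.3.1:

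- Add: *The exception does not apply to an abnormality that meets the DILI criteria in Section 8.4.7.*
- Against the other triggers, limit the exception to clinically nonsignificant abnormalities. If treated, asymptomatic uric acid changes are meant to be excepted, name them.
- Point to Section 8.4.7 instead of 8.4.1.

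Enrollment status is not stated. Amendment 4 is dated June 2025, against an original protocol of May 2022 and a planned study duration of about 38 months, so escalation may be complete. In that case, leave 4.3.1 alone, flag in the 9.6.1 DLT listing any Cycle 1 Grade 3/4 laboratory event whose status depends on the reading, and give the DLT rate both ways. Do not reclassify an event silently: the study is open-label and the data may already be known.

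The cost is one or two sentences and a corrected cross-reference, or one flag column for 6 to 12 participants. The downside is that the reported DLT rate may rise if such an event occurred, and with 3 to 6 participants per dose the change would be visible.
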